### **Reference test**

The reference standard RT-PCR (WHO EUL or FDA EUA approved), where possible, will be performed at an accredited/certified reference laboratory under routine quality control (see section 6 for procedures details). In case of a first indeterminate result, the test may be repeated a second time from the stored left-over sample as per local procedure. (SITE to adapt if necessary)

### **Flow and timing**

With a prospective design, the sample for the index test will be collected in parallel to the sample that will be used for the reference test, so disease progression bias is not a concern. Samples for RT-PCR reference test will be transported from the collection sites to the reference/testing laboratory. Therefore, control measures will be implemented to ensure the quality of specimens during transport. (SITE to adapt if necessary)

If frozen specimens will be used, where possible, to avoid tempering with the integrity of biobanks by continuous freezing and thawing, frozen specimens will be retrieved from the freezers once and batch tested immediately after thawing.

### **Independence of the investigators from manufacturers**

All aspects of the study, including specimen collection, testing, data entry, and data analysis, will be performed independently of the manufacturer of the molecular POC being evaluated. All de-identified clinical and laboratory data will be analysed by FIND and the study team. Both organizations do not have any financial ties/commercial interests or personal conflicts of interest related to any participating test manufacturers.

### **Handling of discordant results**

Discordant results between standard RT-PCR test and index test will not be investigated, as PCR is considered the reference test.

If frozen specimens will be used, discordant results between initial RT-PCR (before freezing and biobanking) and repeated RT-PCR (on thawed specimen selected for the study) may be further investigated.

## **4.4 Randomisation**

Not applicable for this study.

#### **4.5 Blinding Procedure**

Blinding is not required for this study.

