## Schedule of Activities / Sample Flow

Procedures	Day of Enrolment	Timepoint 2	Notes
Inclusion and exclusion criteria verification	X		
Informed consent and participant enrolment	X		
Participant clinical information collection	X		
Sample collection for reference and index test	X		
Index test performance (molecular POC)	X		Sample must be processed according to manufacturer's instructions (within 3h after collection)
Reference test performance (RT-PCR)	X	X	RT-PCR may be performed on another day or in batch (if not used for diagnosis), depending on site's workload/workflow
Ease-of-Use questionnaire completion	n/a	n/a	To be completed by Molecular POC device operators by the end of the study
Sequencing of RT-PCR positive samples		X	Samples may be batched and processed according to site-specific procedures and frequency
Completion of CRFs, including OpenClinica data entry	X	X	Some data may become available later (e.g., sequencing result)
ICFs, CRFs review and study data QC by Principal Investigator or designee	X	X	Data accuracy and quality should be verified at least on a weekly basis
Adverse Event (AE)/Serious Adverse Event (SAE) review	X	X	Limited scope, see Appendix 2

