### **Index test**

There will be no risk of index test results review bias as result interpretation is performed directly by the device and the personnel operating the device will only need to record the results as they are.

To avoid the risk of sample degradation and to comply with the intended use of the device as POC, the operator will run the test within maximum 3 hours after sample collection or as per instructions agreed with the specific device manufacturer.

Ideally, the molecular POC device will be placed in the same room where specimen collection takes place; in case this will not be possible, the device will be placed in dedicated laboratory facilities close (next door) to participants recruitment/sampling location.

Should the test fail, no repetition will be performed. The result will be recorded as reported by the device (e.g., failed, invalid). This will prevent that molecular POC devices allowing test repetition from left-over material without the need of collecting a new specimen may be favoured compared to POC requiring a new specimen for test repetition, like Nudge test.

Standardization of device operation by different users, part of the study team, will be ensured with proper training at the beginning of the study. Proficiency and/or competency assessments will be conducted before initiating and/or during the study at discretion of FIND study team. (SITE-specific

procedures may be added.) As part of the training, molecular POC operators will be instructed to perform the test after all relevant samples will be collected and the study participant will have left the sample collection/testing area. Additionally, the molecular POC testing will be done in the absence of the treating clinician to avoid that the results of the molecular POC are mistakenly used or influence the clinical decision-making process.

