## 6.2 Reference Standard Test and Index Test Procedures

The **reference test** will be one of the FDA/WHO EUA/EUL approved assays detecting SARS-CoV-2 RNA, as recommended by WHO EUL guideline “Instructions and requirements for Emergency Use Listing (EUL) Submission: In vitro diagnostics detecting SARS-CoV-2 nucleic acid or antigen”, unless importation or supply chain issues prevent the use of any of such tests in specific settings selected for the evaluation. In this case, other comparable RT-PCRs might be implemented throughout the study provided they are considered equivalent in respect to the study, as long as it is a country-approved method. (SITE to add specific details on their reference RT-PCR test). The respiratory sample for the reference test will be processed by trained personnel according to the specific Standard Operating Procedure (SOP) in place (the same day of collection or the next day, depending on site workflow). The result will be recorded in the corresponding Case Report Form (CRF).

If possible, the same site-specific RT-PCR protocol will be used for the entire POC evaluation, to ensure consistency throughout the study.

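### Blinding is waived for both tests, which leaves borderline and indeterminate RT-PCR results open to being called or repeated with knowledge of the index result

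*Protocol*

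**What the plan says.** Section 4.5 consists of one statement: "Blinding is not required for this study". It covers both tests and gives no reason.

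Section 4.3 contains the protocol's argument on review bias. For the index test it says "There will be no risk of index test results review bias as result interpretation is performed directly by the device". Its paragraphs on the reference test and on flow and timing say nothing about whether the people who call the RT-PCR may know the index result. For an unclear reference result the rule is: "In case of a first indeterminate result, the test may be repeated a second time from the stored left-over sample as per local procedure". Sites may adapt this.

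On timing, section 4.3 says of the index test that "the operator will run the test within maximum 3 hours after sample collection", or as agreed with the manufacturer. Section 6.2 has the reference sample processed "the same day of collection or the next day, depending on site workflow". The Schedule of Activities adds: "RT-PCR may be performed on another day or in batch (if not used for diagnosis), depending on site's workload/workflow".

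Section 10.2 has reference and index results recorded under the same participant identifier and entered in a site-specific OpenClinica database. It mentions individual password-protected accounts but does not say who may see which result.

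Table 4 in section 8.2 restricts the per-protocol population to participants with valid results on both tests. Section 8.3 uses that population for Endpoint 1.1.

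**The concern.** An accuracy study rests on the reference result being reached independently of the index result. The protocol explains why the index reading cannot be swayed and then waives masking for both tests. The reference side has two human decisions that a device reading does not have: how to call a borderline RT-PCR, and whether to repeat an indeterminate one. If the index result is known when either is made, the resolution can drift towards agreement.

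The second decision also settles whether a specimen is analysed at all, because an indeterminate result that is never resolved is not valid and leaves the per-protocol set. The primary estimates are expected to rest on very few errors, about 3 false negatives and 1 false positive, so a handful of such decisions can be visible in the result. The SAP cannot repair this afterwards, since masking has to be in place when results are read.

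**Working it through.** **Step 1: can the index result come first?** Index test: within 3 hours of collection, or as agreed with the manufacturer (section 4.3). RT-PCR: same or next day (section 6.2), or another day or in batch when it is not used for diagnosis (Schedule of Activities). So it can come first. The documents do not say how often it does.

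**Step 2: is there a barrier between the index result and the RT-PCR reader?** The statements closest to a safeguard are these:

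| Statement | What it protects | Masks the RT-PCR reader? |
|---|---|---|
| Index result read by the device (4.3) | Index reading | No |
| Index testing done away from the treating clinician (4.3) | Patient management | No |
| Accredited laboratory under routine quality control, where possible (4.3) | Technical quality | No |
| Index/RT-PCR discordants not investigated (4.3) | Reference results already final | No, but it closes later revision |
| A valid positive RT-PCR makes a confirmed case (6.2) | Reference results already final | No, but it closes later revision |

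The last two rows confine the exposure to the stage before a valid RT-PCR result exists, that is, to initial borderline or indeterminate results.

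**Step 3: size.** Inputs from section 8.1: sensitivity 97% with 100 RT-PCR positives, so 97 detected and 3 missed; specificity 99% with 100 negatives, so 1 false positive. Sensitivity = a/(a + c), with Wilson intervals as in section 8.3. The rate of indeterminate results is not given, so k, the number of index-negative positives left indeterminate and dropped, is an assumption. I take k = 1 to 3; 3 is the ceiling because only 3 are missed.

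| k | Sensitivity | Wilson 95% CI |
|---|---|---|
| 0 | 97/100 = 97.0% | 91.5% to 99.0% |
| 1 | 97/99 = 98.0% | 92.9% to 99.4% |
| 2 | 97/98 = 99.0% | 94.4% to 99.8% |
| 3 | 97/97 = 100% | 96.2% to 100% |

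Each such specimen is worth about 1 percentage point.

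Section 3.3 ends the study only when the required number of positives is reached, so a dropped positive would be replaced. That does not undo the shift. With one dropped and one replacement detected with probability 0.97, the expected figure is (97 + 0.97)/100 = 97.97%.

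Specificity: if the single expected false positive were left indeterminate and dropped, 99/100 = 99% becomes 99/99 = 100%.

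The effect is not symmetric. One additional borderline specimen that is index-positive and resolved as RT-PCR positive moves sensitivity only from 97/100 to 98/101 = 97.03%. The risk lies mainly in how the few disagreeing specimens are resolved.

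**Step 4: effect of the fix on size.** The screening figure of 2171 in section 8.1 reproduces as the smallest n with (0.05n − 100)/√(n × 0.05 × 0.95) ≥ 0.8416. At n = 2171 this is 8.55/10.155 = 0.842; at 2170 it is 0.837. None of its inputs depends on masking, so it does not change.

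**The case against.** The best defence is that the two tests are already largely separate. The RT-PCR uses the routine diagnostic sample, is sent to a reference or testing laboratory and is processed by trained staff under an SOP. Where possible it "will be performed at an accredited/certified reference laboratory under routine quality control". The index test is run by device operators at or next to the collection point, and its result is not used in care. No section describes the index result reaching the RT-PCR reader. The optional repeat is tied to local procedure, so the word may simply accommodate different laboratory SOPs. Detailed procedures are left to the Study Manual, and a statement that blinding is not required does not forbid masking.

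Much of this stands, and it limits the size of the concern. It does not remove it. Separation in practice is not a rule, accreditation is conditional, the results share a database, and under section 4.5 nothing obliges the manual or a local procedure to withhold the index result.

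A reader might also infer stronger points that the documents do not support:

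- **That weak RT-PCR positives with a negative index result could be re-read as negative, lifting sensitivity from 97% to 100%.** The protocol closes this route: "Discordant results between standard RT-PCR test and index test will not be investigated, as PCR is considered the reference test". A valid positive stands as a confirmed case, and a repeat is foreseen only after an indeterminate result. The k = 3 row above reaches 100% by a different mechanism, non-resolution of indeterminates, and is a ceiling rather than an expectation.
- **That the shared swab for the Mirai test creates review bias.** Sharing a sample does not tell the RT-PCR reader the index result.
- **That known RT-PCR status of banked specimens biases the index test.** The device reads that result and a failed test is not repeated, so prior knowledge cannot change it.
- **That the index result usually comes first, or that the waiver saves nothing.** The documents support only that it can come first, with batch RT-PCR limited to tests not used for diagnosis. They give no cost information.

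**Conclusion.** The concern holds in a limited form. Section 4.5 waives masking outright, section 4.3 answers review bias for the index test only, and nothing in the protocol keeps the index result from those who call the RT-PCR or decide on a repeat. Followed as written, the plan leaves borderline calls and the handling of indeterminates open to the index result, and those decisions affect who enters the primary analysis.

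The plausible direction is towards agreement. The size is about 1 percentage point of sensitivity per index-negative positive left unresolved, and at most 3 points at the protocol's own assumptions. This rests on two things the documents do not give: how many RT-PCR results are indeterminate or borderline at first, and whether staff would see the index result and act on it. If indeterminates are rare or the laboratory is separate in practice, the effect may be nil. The change is worth making because it is a small one and the study presents itself as an independent evaluation.

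**What to change.** 1. **Section 4.5.** Replace the waiver with a rule that RT-PCR laboratory staff have no access to the index result until the RT-PCR result, including any repeat, is final.
2. **Section 4.3, reference test.** Replace the optional repeat with a fixed rule for the study's reference classification: every first-indeterminate RT-PCR is repeated once where left-over sample exists, regardless of the index result, and stays indeterminate if the repeat is indeterminate too.
3. **Section 4.3, discordant results, frozen specimens.** The protocol allows further investigation when the RT-PCR before freezing and the RT-PCR on the thawed specimen disagree. Apply the same masking to that investigation.

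The cost is protocol wording, role permissions in the existing database and a few repeat RT-PCRs of a kind already allowed. The targets of 100 positives and 100 negatives and the screening figure of 2171 are unchanged. The use of results in care is not affected, because index results already play no part in it.

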### **5 Participant Discontinuation/Withdrawal**

#### **5.1 Participant Discontinuation/Withdrawal from the Study**

A participant may be withdrawn at any time at the discretion of the Investigator for safety, behavioural, compliance, or administrative reasons.

Depending on site-specific informed consent:

- If a participant withdraws consent for disclosure of future information, FIND may retain and continue to use any data collected before such a withdrawal of consent.
- If a participant withdraws from the study, he/she may request destruction of any data collected for the study, and the Investigator must document this in the site study records.
- If a participant withdraws from the study, he/she may request destruction of any samples taken and not tested, and the Investigator must document this in the site study records.
- If a participant withdraws from the study, he/she may request destruction of any residual samples stored, and the Investigator must document this in the site study records.

(SITE to adapt and clarify what happens to samples and data after participant's withdrawal in agreement with ICF)

#### **5.2 Lost to Follow Up**

Not applicable for this study.

## 6 Study Procedures

Study procedures and their timing are summarized in the Schedule of Activities. Protocol waivers or exemptions are not allowed.

Adherence to the study design requirements is essential and required for study conduct.

All screening evaluations must be completed and reviewed to confirm that potential participants/specimens meet eligibility criteria. The investigator will maintain a screening log to record details of all participants screened and to confirm eligibility or record reasons for screening failure, as applicable.

Detailed study procedures will be described in the Study Manual.

### 6.1 Specimen Collection, Handling, Transport and Storage

Participants will be recruited at the study sites (SITE to add specific details where participants will be recruited). Participants who meet all inclusion and none of the exclusion criteria and showing interest in participating in the study, will be informed by an authorized study site team member. All elements of the consent form will be carefully, patiently, and clearly explained to the prospective subject, providing him/her sufficient time to ask questions and to make his/her decision. If he/she decides to participate, the participant and the authorized study site team member, responsible for conducting the informed consent process, will sign the consent form. Participants will only be enrolled to the study after signing the informed consent.

Selected sites have established procedures for respiratory sample collection for SARS-CoV-2 diagnostic testing. Health care workers collecting samples are already trained specifically in respiratory sample collection and handling techniques and will be wearing appropriate personal protective equipment (PPE) at the time of sample collection. A respiratory sample for reference testing will be collected for routine testing on the day of enrolment as per clinical routine. A study-specific respiratory sample (e.g., nasal swab or as per index test manufacturer's claim) will be collected as well on the same day, unless the index test can be performed on the same sample as the reference test, and used to perform molecular POC testing immediately after collection (Table 2). Site-specific instructions on temporal sequence for specimens' collection for reference and index tests will be followed.

The novel molecular POC assay will be performed within designated SARS-CoV-2 isolation zones directly at recruitment/sampling location or in dedicated laboratory facilities close (next door) to participants recruitment/sampling location, ensuring safety for everyone in that area and timely processing of the index test, as per IFU. (SITE to add specific details on molecular POC location). Operators running the index test and lab personnel will be wearing appropriate PPE per clinical routine, and the testing will not add any new biosafety hazard to routine clinical practices.

Participants will be diagnosed based on RT-PCR results performed on the routine diagnostic sample (nasopharyngeal swab) and clinical signs and symptoms by their treating physician; results of novel molecular POC devices tests will not be used for clinical management.

**Table 2:** Sample types and testing

Sample Type	Testing	Additional Notes
Routine RT-PCR Nasopharyngeal Swab (x1)	
 
Molecular reference testing for COVID-19 (RT-PCR) as per standard of care (usually placed in standard VTM/UTM).
 
Mirai device testing for study purposes (processed as recommended by test manufacturer in the IFU).
 
	Transported at 2-8°C to reference/testing laboratory after collection. Leftover sample after RT-PCR testing will be kept at -70°C or lower until the study ends or longer depending on the site-specific informed consent. Leftover samples may be used for repeating RT-PCR testing and/or genomic sequencing following positive RT-PCR results. SITE to clarify whether the remaining specimen may be stored in biobank for future studies.
Molecular POC devices specific respiratory sample: 
 
Nasal Swab for Nudge and GenomEra (x1 as per assay IFU);
 
Nasopharyngeal Swab for Mirai (the same sample for reference test can be used)
 
	Nudge, Mirai and GenomEra devices testing for study purposes (processed as recommended by test manufacturer in the IFU).	Processed immediately (within 3h max from collection or as per instructions agreed with the specific device manufacturer) at the collection site or at dedicated laboratory facility close (next door).

If frozen or same-day fresh left-over specimens will be used, specimen type and collection/storage medium must be validated by FIND for evaluation with the specific molecular POC. Device manufacturer will be consulted to this purpose (Table 3). Where possible, to avoid tempering with the integrity of biobanks by continuous freezing and thawing, frozen specimens will be retrieved from the freezers once and batch tested.

**Table 3.** Specimen types and volumes required for molecular POC devices

Type of specimen	Specimen type required for POC test			Volume of specimen required per test		
	DnaNudge	Mirai	GenomEra	DnaNudge	Mirai	GenomEra
Frozen specimen (from biobank)	Specimen in UTM/VTM	Specimen in UTM/VTM	Specimen in Copan eNAT	Pipette 200-250ul VTM/UTM to swab chamber.	Mix 200 ul of a UTM with sample and add 800ul of the GenPad SSB	50ul of specimen collected in Copan eNAT
Same-day fresh specimen (left-over from diagnostic laboratory)	Nasal swab	Nasopharyngeal swab	Nasal swab	200-250ul VTM/UTM	200ul	50ul

## 6.2 Reference Standard Test and Index Test Procedures

The **reference test** will be one of the FDA/WHO EUA/EUL approved assays detecting SARS-CoV-2 RNA, as recommended by WHO EUL guideline “Instructions and requirements for Emergency Use Listing (EUL) Submission: In vitro diagnostics detecting SARS-CoV-2 nucleic acid or antigen”, unless importation or supply chain issues prevent the use of any of such tests in specific settings selected for the evaluation. In this case, other comparable RT-PCRs might be implemented throughout the study provided they are considered equivalent in respect to the study, as long as it is a country-approved method. (SITE to add specific details on their reference RT-PCR test). The respiratory sample for the reference test will be processed by trained personnel according to the specific Standard Operating Procedure (SOP) in place (the same day of collection or the next day, depending on site workflow). The result will be recorded in the corresponding Case Report Form (CRF).

If possible, the same site-specific RT-PCR protocol will be used for the entire POC evaluation, to ensure consistency throughout the study.

